## 7.2 Randomization

After registration, research staff will randomize patients via MSK's secure Clinical Research Database (CRDB) using permuted blocks of random length. The allocation ratio will be 1:1 for ACU:OPI. Using the institutional randomization standard procedure with random blocks for RCTs will ensure full allocation concealment. Randomization will be stratified by study site, primary cancer diagnosis (MM versus HD versus NHL) and transplantation setting (inpatient versus outpatient) to ensure these characteristics are comparably distributed between the two study arms.

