## **14.0 BIOSTATISTICS**

This is a multicenter, two-arm randomized controlled trial to compare the effects of two pain management strategies on opioid use, symptom burden, and other patient-reported outcomes among patients receiving high-dose chemotherapy (HiChemo) followed by HSCT. Opioid-naïve adult multiple myeloma, Hodgkin disease, and non-Hodgkin lymphoma patients undergoing HiChemo followed by HSCT will be randomized (at 1:1 ratio, see Section 7.2) to receive either acupuncture as a first-line pain preventive measure during HiChemo with opioids as back-up pain treatment (ACU), or opioids as first-line pain treatment (OPI). Study outcomes will be measured at pre-HiChemo baseline and at Days 7, 15, 30, and 90 after the first dose of HiChemo, with the Day 7 (short-term) and Day 90 (long-term) outcomes of particular interest. We expect to accrue approximately 12 patients per month, and we anticipate the study will be open to enrollment for approximately 30 months. We expect the

total study duration to be 3 years.

**14.1. Sample Size Considerations.** This study has 3 primary endpoints: opioid use at Day 7, opioid use at Day 90, and symptom burden at Day 7. The statistical plan takes that into consideration. Our overall Type I error rate for testing these 3 primary endpoints is set to alpha = 0.05. To maintain this Type I error rate, we will allocate alpha = 0.02 to each of the tests of opioid use at Day 7 and at Day 90, and we will allocate alpha = 0.01 to the test of symptom burden at Day 7.

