For our sample size/power considerations for comparing symptom burden between ACU vs. OPI at Day 7, we calculated the smallest standardized effect size (aka, Cohen's d) we will be able to detect with 80% power, given our sample sizes of 150 in each of the two arms. To estimate this smallest detectable effect size, we used the methods of Lu, Luo, & Chen (2008), which describes sample size calculations for a class of analyses called the “mixed model for repeated measures” (MMRM) in randomized clinical trials with participant attrition. Our LMM analyses fall under this MMRM class of analyses. Using the “power.mmmr”

function from the R package “longpower”, we applied the formulas in Lu et al. (2008) to our study design and assumptions to derive the smallest detectable effect size for the coefficient of the time-by-arm interaction term in our LMM (with time including only the Day 0 and Day 7 assessments, see Section 14.2), which we transformed to represent the standardized mean difference (aka, Cohen’s  $d$ ) of the changes in symptom burden from baseline between the two arms at Day 7 post-HSCT. With 150 participants in each of the two arms, we will have power of 0.80 to detect an effect size for symptom burden as small as 0.41 (standardized difference, Cohen’s  $d$ ) at Day 7 between acupuncture vs. usual care, assuming 10% attrition, correlation between baseline and Day 7 symptom burden scores of 0.50, and two-sided alpha of 0.01. The MDASI-BMT Total Symptom Severity score does not have an empirically-established minimum clinically important difference (MCID). A research-based rule-of-thumb for PRO instruments lacking empirical MCIDs is to adopt a standardized difference of 0.50 as the MCID. Given our detectable effect size of 0.41, we will be able to detect a MCID in symptom burden between the two arms.

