**14.2.2. Specific Aim 1 Analysis Methods.** To test Aim 1 hypotheses, we will test whether ACU has fewer opioid users compared to OPI at Day 7 (Hypothesis 1a) and at Day 90 (Hypothesis 1b) using separate but similar logistic regression models. Each model will predict opioid use at the given time point as a function of treatment arm (ACU vs. OPI), controlling for the randomization stratification variables (study site and cancer diagnosis). To test whether ACU reduces symptom burden at Day 7 compared to OPI (Hypothesis 1c), we will use a LMM to model the baseline and Day 7 MDASI-BMT Total Symptom Severity scores as a function of study arm (ACU vs. OPI), time (Day 0 and Day 7), and the arm-by-time interaction (coefficient of interest), controlling for the randomization stratification variables.

**14.2.3. Specific Aim 2 Analysis Methods.** For the Aim 2 hypotheses we will first test (Hypothesis 2a) whether mean pain scores among ACU patients were non-inferior to those among OPI patients (within a non-inferiority margin of 0.34 standard deviations) at Day 7 (key Aim 2 endpoint) using a LMM containing arm, time (Days 0 and 7), and the arm-by-time interaction as predictors, controlling for the randomization stratification factors. That is, if the mean Day 7 pain score in the ACU arm is not significantly ( $p < 0.025$ ) more than 0.34 standard deviations higher than the mean OPI pain score, then we will consider ACU to be non-inferior to OPI with respect to Day 7 pain control. A similar analysis will be performed for the Day 90 pain scores. For Hypothesis 2b, we will estimate mean differences (and 95% confidence intervals) between ACU vs. OPI side effect ratings, PROMIS-29 scores, and PROMS scores using separate linear mixed models for the Day 7 and Day 90 outcomes, controlling for the randomization stratification variables and baseline score (when relevant). We will have 80% power to detect unadjusted differences between study arms on these outcomes as small as 0.34 SD (i.e., Cohen's  $d = 0.34$ ) using two-sided tests and  $p < 0.05$ . By convention, this effect size is between a small (i.e.,  $d = 0.20$ ) and moderate ( $d = 0.50$ ) effect size. We will have power to detect smaller effect sizes in the covariate-adjusted regression analyses described above, but we have insufficient preliminary data on which to base estimates of these adjusted effect sizes.

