We will adjust all comparisons between the two treatment arms for the randomization stratification factors - study site and primary cancer diagnosis (MM versus HD versus NHL) - by including them as fixed effects in our statistical models.

**14.2.4. Exploratory Aim 1, Mediation.** We will explore potential causal mechanisms by testing mediation hypotheses (e.g. test whether the effect of treatment on Day 90 opioid use is mediated through the effect of treatment on Day 7 opioid use). We will use the approach to testing mediation hypotheses outlined in Imai, Keele, & Tingley (2010) in which a series of models are fit that allow estimation of the total, direct, and indirect (i.e., through the mediator) effects of treatment arm on Day 90 opioid use.

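### Stratification factors entered as main effects give almost no adjustment of the arm-by-time test of Day 7 symptom burden (Hypothesis 1c); add factor-by-time terms

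*Combined protocol and SAP*

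**What the plan says.** Section 7.2: "Randomization will be stratified by study site, primary cancer diagnosis (MM versus HD versus NHL) and transplantation setting (inpatient versus outpatient"), and "The allocation ratio will be 1:1 for ACU:OPI".

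Section 14.1 names symptom burden at Day 7 as one of three primary endpoints: "we will allocate alpha = 0.01 to the test of symptom burden at Day 7". Its precision statement reads "With 150 participants in each of the two arms, we will have power of 0.80" for a standardised difference of 0.41, "assuming 10% attrition, correlation between baseline and Day 7 symptom burden scores of 0.50, and two-sided alpha of 0.01".

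Section 14.2.2 models the baseline and Day 7 scores on arm, time "and the arm-by-time interaction (coefficient of interest), controlling for the randomization stratification variables". Section 14.2.3 gives the Day 7 non-inferiority test of pain (Hypothesis 2a) the same two-time-point form and says the Day 90 test will be similar. It closes with a general promise: "We will adjust all comparisons between the two treatment arms for the randomization stratification factors", carried out "by including them as fixed effects in our statistical models".

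Arm-by-time is the only interaction named for these models. Section 14.4 keeps every randomised patient with a valid baseline score in the symptom-burden analysis, so patients with a baseline score only are included.

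**The concern.** The tested coefficient is the arm difference in mean change from baseline to Day 7. A factor such as site or diagnosis is constant within a patient. Entered as a main effect, it explains level, which the change contrast has already removed, and says nothing about change. The model therefore appears to adjust the comparison for the strata but leaves it essentially as it was.

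This matters when the strata predict how far symptoms rise. Stratified randomisation balances the arms on those factors and so reduces the true sampling variance of the arm difference. The model does not take that reduction into account and reports a standard error that is too large. The affected test carries the smallest alpha of the three primary tests. In Hypothesis 2a the same overstatement would make non-inferiority harder to show.

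The other comparisons differ. The logistic models for Hypotheses 1a and 1b, and the single-time-point models for 2b with baseline as a covariate, let the listed factors act directly on the outcome being compared.

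**Working it through.** **Inputs from the plan.** 150 patients per arm, 10% attrition, baseline to Day 7 correlation 0.50, two-sided alpha 0.01, power 0.80 (Section 14.1). Normal quantiles: 2.576 and 0.842.

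**Input not in the plan.** R² is the share of the variance in change explained by the strata. I assume 0 to 20%.

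**Step 1: reproduce the plan's figure.** With baseline-only patients kept, the variance factor is 0.50² + (1 − 0.50²)/0.9 = 1.0833. The detectable difference is (2.576 + 0.842) × √(2 × 1.0833/150) = 0.411, which agrees with the stated 0.41. No stratification adjustment enters this figure. Below I use the simpler basis of 135 completers per arm. At correlation 0.50 the variance of change is 2 × (1 − 0.50) = 1, so SE = √(2/135) = 0.1217 and the detectable difference is 3.417 × 0.1217 = 0.416.

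**Step 2: the cancellation.** Write the two scores of patient i as

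- baseline = a + b·arm + s(stratum) + error
- Day 7 = a + b·arm + t + c·arm + s(stratum) + error

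Their difference is t + c·arm + error. The stratum term s is gone, so with complete data it cannot affect the estimate of c or its SE. Fits to simulated data sets (300 patients) confirm this:

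| Data set | No strata: estimate (SE) | Main effects: estimate (SE) | Factor-by-time: estimate (SE) |
|---|---|---|---|
| Complete, unstructured | 0.1200 (0.1240) | 0.1200 (0.1240) | 0.1240 (0.1217) |
| Complete, compound symmetry | 0.2029 (0.1162) | 0.2029 (0.1162) | 0.1999 (0.1134) |
| 10% missing, unstructured | 0.2502 (0.1230) | 0.2382 (0.1228) | 0.2290 (0.1175) |
| 10% missing, compound symmetry | −0.1608 (0.1179) | −0.1529 (0.1178) | −0.1541 (0.1111) |

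With 10% missing, across scenarios of 3,000 simulated trials each, main effects moved the coefficient by 0.004 to 0.011 SD on average (3 to 9% of an SE) and by at most about 0.05 SD.

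**Step 3: the consequence if strata predict change.** Let k = √(1 − R²). As written, the reported SE is 0.1217 but the true one is 0.1217k. Then:

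- actual alpha = 2 × [1 − Φ(2.576/k)]
- power as written = Φ[(d/0.1217 − 2.576)/k]
- power with factor-by-time terms = Φ[d/(0.1217k) − 2.576]
- detectable difference as written = 0.1217 × (2.576 + 0.842k)
- detectable difference with factor-by-time terms = 0.1217k × 3.417

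Power is taken at d = 0.416:

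| R² | k | Actual alpha as written | Power as written | Power with terms | Detectable as written | Detectable with terms |
|---|---|---|---|---|---|---|
| 0 | 1.000 | 0.0100 | 80% | 80% | 0.416 | 0.416 |
| 5% | 0.975 | 0.0082 | 81% | 82% | 0.413 | 0.405 |
| 10% | 0.949 | 0.0066 | 81% | 85% | 0.411 | 0.395 |
| 20% | 0.894 | 0.0040 | 83% | 89% | 0.405 | 0.372 |

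**Step 4: check by simulation.** Blocks were permuted within site by diagnosis, with 3,000 trials per scenario and a Monte Carlo SE of about 0.002. With strata explaining about 9% of the variance in change, rejection under the null with main effects was 0.0073 (complete data) and 0.0063 (10% missing at random). With factor-by-time terms it was 0.0103 and 0.0100. When strata shifted both visits equally (R² of change = 0), main effects gave 0.0100 and 0.0083, against 0.0100 and 0.0087.

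**The case against.** **The text does not say main effects only.** This is true. Controlling for a factor by a fixed effect does not exclude its interaction with time. But the plan names its interactions where it wants them (arm-by-time here, variable-by-arm in Section 14.2.5) and names none between a stratification factor and time. Main effects are the natural reading. If interactions are intended, one added line settles it.

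**The factors are not wholly inert.** This also stands. A reader might infer that they can never change the tested coefficient. That holds only with complete data. With 10% attrition and baseline-only patients kept, it moves slightly.

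**Loss of precision is not established.** This stands too. A reader might infer that the test is conservative as a matter of fact. That needs strata that predict change rather than level, and no document gives the figure. There are reasons to expect something above zero. Baseline precedes chemotherapy, so differences in toxicity would show at Day 7. Section 10.0 also anchors Day 0 to different drugs in different regimens, and the regimens differ by diagnosis. Neither reason gives a size.

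**The test does what Section 14.1 claims.** This is correct. Type I error is not inflated, and power as written is 80% or more at the planned effect. At the 0.50 SD that the plan takes as clinically important, power as written is already about 94 to 96%. On the basis that reproduces 0.41, the extra terms add about 0.7, 1.2 or 1.9 percentage points at R² of 5, 10 or 20%.

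**Conclusion.** The point holds as one of efficiency and of agreement between the stated and the actual adjustment. On the natural reading, the Hypothesis 1c comparison and the same-form comparisons of Hypothesis 2a are essentially not adjusted for the strata, contrary to the promise for all comparisons.

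The documents do not support calling the test invalid or underpowered: it keeps its level and its stated power, and the 0.41 reproduces without any adjustment. Nor is it right to set the detectable difference of 0.416 at R² = 0 against the adjusted figures at higher R², because the unadjusted figure falls too. At equal R² the gain is 0.413 − 0.405 = 0.008, 0.411 − 0.395 = 0.016 and 0.405 − 0.372 = 0.033 SD for 5, 10 and 20%.

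The cancellation follows from the model form and needs no assumption about R². The sizes depend on the assumed R², a correlation of 0.50 and 135 completers per arm. The effect on Hypothesis 2a has the same direction and was not quantified.

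**What to change.** In Sections 14.2.2 and 14.2.3, state that each stratification factor and its interaction with time enter the two-time-point mixed models for Hypotheses 1c and 2a. Keep patients with a baseline score only, as Section 14.4 requires. An ordinary regression of the Day 7 score on arm and strata is not an equal substitute: it would drop those patients, and it would ignore the baseline score unless that were added.

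With two sites and three diagnoses this adds 1 + 2 = 3 interaction parameters, or 4 if transplantation setting is included. Sections 14.2.2 and 14.2.3 list only site and diagnosis, while Section 7.2 also stratifies by setting. That separate discrepancy should be resolved in the same edit.

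The cost is a line or two of wording and these few parameters in about 270 patients with Day 7 data. No new data are needed. The change should be made before any analysis by arm, so that the choice of terms is not post hoc.

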For Aim 2, we will test whether mean ACU pain scores are non-inferior to mean OPI pain scores at two timepoints, Day 7 and Day 90. To limit the type I error rate for this family of two tests to 0.05, we will use a significance threshold for each test of 0.025. The Aim 2 key endpoint is Day 7 pain scores, since pain due to HiChemo is expected to peak around Day 7 and resolve well before Day 90 for both study arms. We present power considerations below for the Day 7 non-inferiority test. The same assumptions apply to the Day 90 test; however, we expect ACU pain scores to be well within our non-inferiority margin by Day 90. We will have 80% power to find mean ACU pain scores non-inferior to mean OPI pain scores within a non-inferiority margin of 0.34 standard deviations (SD), assuming 300 patients, 10% attrition, and one-sided significance threshold of 0.025. Our non-inferiority margin (0.34 SD) is smaller than the typical minimum clinically important difference (MCID) for self-report measures (i.e., MCID = 0.50 SD for BPI). Therefore, this margin represents an acceptable pain control benchmark for ACU in comparison to OPI.

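### The pain non-inferiority rule in section 14.2.3 is reversed: an ACU arm worse by exactly the 0.34 SD margin would pass 97.5% of the time, not 2.5%.

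*Combined protocol and SAP*

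**What the plan says.** Hypothesis 2a (section 2.0) is that ACU is not inferior to OPI on pain at Days 7 and 90. Section 14.2.3 first describes the test in conventional terms: the analysis asks "whether mean pain scores among ACU patients were non-inferior to those among OPI patients (within a non-inferiority margin of 0.34 standard deviations"), using a linear mixed model.

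The next sentence turns this into a decision rule. Its condition opens "if the mean Day 7 pain score in the ACU arm is not significantly", with significance judged at the 0.025 level. The threshold and the conclusion come later in the same sentence: "more than 0.34 standard deviations higher than the mean OPI pain score, then we will consider ACU to be non-inferior to OPI". Day 90 is to be analysed in a similar way.

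Section 14.1 gives the design figures for the same test: "We will have 80% power to find mean ACU pain scores non-inferior to mean OPI pain scores" with a margin of 0.34 SD, "assuming 300 patients, 10% attrition, and one-sided significance threshold of 0.025". It sets 0.025 for each of the two tests so that the family of two is held to 0.05. It defends the margin as smaller than a minimum clinically important difference, given as "MCID = 0.50 SD for BPI".

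No null and alternative hypotheses and no confidence-limit criterion for pain appear elsewhere. The 95% confidence intervals mentioned in section 14.2.3 belong to Hypothesis 2b.

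**The concern.** A non-inferiority claim requires rejecting the null hypothesis that ACU is worse by at least the margin. The written rule takes the opposite null, that ACU is worse by no more than the margin, and counts failure to reject it as success. The 0.025 then limits the chance of wrongly calling ACU inferior. It no longer limits the chance of wrongly calling it non-inferior, which is the error section 14.1 says it controls. The rule also rewards imprecision: the fewer the evaluable patients, the easier it is to pass.

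The trial's overall objective has two parts: less opioid use, and pain control that is not sacrificed to get it. Hypothesis 2a is the only formal test of the second part. An opioid-sparing result is hard to interpret if the pain safeguard usually passes an arm that is worse by the plan's own clinically important difference. Leaving sections 14.1 and 14.2.3 in conflict also allows either rule to be chosen once the results are known.

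**Working it through.** **Inputs**
- Margin 0.34 SD, one-sided 0.025, 300 patients, 10% attrition: section 14.1.
- 135 evaluable per arm: 300 × 0.90 / 2, as section 14.1 also states.
- Clinically important difference 0.50 SD: section 14.1.
- True difference for the power figure: not stated; taken as 0.
- Baseline correlation for pain: not stated. Section 14.1 gives a "correlation between baseline and Day 7 symptom burden scores of 0.50"; the same value is assumed for pain as a sensitivity case.

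**Standard errors (SD units)**
- Unadjusted: √(2/135) = 0.1217.
- Baseline-adjusted, correlation 0.50: √(2 × (1 − 0.5²)/135) = 0.1054.
- Difference in change from baseline (arm-by-time term), correlation 0.50: √(4 × (1 − 0.5)/135) = 0.1217, the same as unadjusted.

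**Reproducing the plan's figure**
- Standard rule, true difference 0: Φ(0.34/0.1217 − 1.96) = 79.8%.
- Margin that gives exactly 80%: (1.96 + 0.842) × 0.1217 = 0.341 SD.
- Written rule, true difference 0: Φ(0.34/0.1217 + 1.96) > 99.99%.

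The stated 80% therefore belongs to the standard rule.

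**Largest observed ACU excess that still passes**
- Written: 0.34 + 1.96 × SE = 0.58 SD (0.55 at the smaller SE).
- Standard: 0.34 − 1.96 × SE = 0.10 SD (0.13 at the smaller SE).

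Using the unadjusted SE, the two rules give opposite verdicts for any observed excess between about 0.10 and 0.58 SD.

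**Chance of declaring non-inferiority at true excess d**

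Written: Φ((0.34 − d)/SE + 1.96). Standard: Φ((0.34 − d)/SE − 1.96). Values in parentheses use SE 0.1054.

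| True excess (SD) | Written rule | Standard rule |
|---|---|---|
| 0 | >99.99% | 79.8% (89.7%) |
| 0.34 (margin) | 97.5% (97.5%) | 2.5% (2.5%) |
| 0.50 (cited MCID) | 74% (67%) | 0.05% (0.03%) |
| 0.58 | 50% (38%) | about 0 |
| 0.68 | 20% (10%) | about 0 |
| 0.80 | 3.4% (0.8%) | about 0 |
| 1.0 | 0.03% (0.001%) | about 0 |

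A simulation of 200,000 draws at the unadjusted SE agreed at 0, 0.34 and 0.50 SD.

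**Sensitivity**
- At the margin d = 0.34, so the first term is zero and the 97.5% versus 2.5% contrast depends on alpha alone.
- At 0.50 SD, a change-score SE at correlation 0.3 (0.144) gives the written rule 80%; a baseline-adjusted SE at correlation 0.7 (0.087) gives 55%. The standard rule stays at or below 0.11%.
- With about half the patients (67 per arm, illustrative), SE = √(2/67) = 0.173 and the written rule passes a 0.50 SD excess 85% of the time.
- Section 14.2.3 does not state sidedness. Read as two-sided 0.025, the written rule passes 98.75% at the margin, and the standard rule has 71% power, which does not match the stated 80%. One-sided 0.025 is the consistent reading.

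**The case against.** The best defence is that this is a slip of wording. The preceding sentence in section 14.2.3 and the whole Aim 2 paragraph of section 14.1 describe a standard non-inferiority test, and moving one word (significantly not more, rather than not significantly more) restores it. An analyst might well run the right test anyway. That is a fair account of how the error arose, but it does not remove it: the sentence is the plan's own definition of success.

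Second, Hypothesis 2a is not a primary test: "This study has 3 primary endpoints: opioid use at Day 7, opioid use at Day 90, and symptom burden at Day 7". Those tests, their alpha split and the sample size are untouched. The large contrasts also require a true excess at or beyond the margin. Section 14.1 does not expect that at Day 90, and nothing in the documents predicts it at Day 7. This limits the reach of the defect. But the margin and beyond are exactly where a non-inferiority test has to protect.

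Three technical points stand as qualifications:
- A true difference of zero is the simplest match to 80% power, not the only one. At SE 0.1054 the standard rule gives 80% at a true difference of about 0.045 SD.
- The written cut-off exceeds 0.50 SD only if the SE is above 0.16/1.96 = 0.082, which for a baseline-adjusted analysis means a correlation below about 0.74.
- The 80% holds when the SD that scales the margin is the Day 7 between-patient SD. If a smaller baseline SD were used, power would fall: at assumed ratios of 0.9, 0.8 and 0.5 it would be 71%, 61% and 29% with the unadjusted SE.

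**Conclusion.** The concern holds, and the sentence must be corrected. As written, the false-positive rate at the margin is 97.5% where section 14.1 promises 2.5%; this needs no assumption beyond reading 0.025 as one-sided. At a true excess equal to the cited 0.50 SD difference, the written rule passes ACU 74% of the time (67% with an assumed baseline correlation of 0.50), against 0.05% (0.03%) for the standard rule. These last figures assume 135 evaluable patients per arm and equal SDs in the two arms. The failure is concentrated between the margin and somewhat beyond the clinically important difference. A grossly inferior arm would still usually be caught. The defect affects Hypothesis 2a at Days 7 and 90 only.

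**What to change.** Replace the decision sentence in section 14.2.3 with wording such as:

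> ACU will be considered non-inferior at Day 7 if the upper limit of the two-sided 95% confidence interval for the ACU minus OPI difference in mean pain score is below +0.34 SD (one-sided p < 0.025 against H0: difference ≥ 0.34 SD). The same rule applies at Day 90.

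Add a clause naming the SD that scales the margin (for example baseline, pooled Day 7 or model-based) and fix that choice before outcomes are compared by arm. The Day 7 between-patient SD is the choice under which the stated 80% stands; with another choice, restate the power. It would also help to say whether the contrast is the Day 7 mean difference or the arm-by-time term, since the two can differ when baseline means are not constrained to be equal.

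The cost is one replaced sentence and one or two clauses. No patients or data are added, and the margin in SD units and the sample size stay as they are.

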## 14.2. Statistical Methods.

**14.2.1. General Approaches.** All analyses will be by intent-to-treat, with patients analyzed as randomized, irrespective of treatment actually received. Demographics and other relevant variables (e.g., number of acupuncture sessions received in the ACU arm) will be summarized by treatment arm using standard descriptive statistics. All data at all assessment time points will be summarized by treatment arm using standard descriptive statistics and plotted to visually assess trajectories over time. In the following subsections, we present specific analysis plans that are tailored to address our specific aim hypotheses, focus on single assessment time points, have relatively straightforward interpretations, and will be used to draw our primary conclusions regarding the Aims of this trial. However, our more general analysis approach will use more complex models to capitalize on the longitudinal nature of the study design and allow us to examine plots of the model-based trajectories of our outcome measures over time by study arm, giving us a visual overview of each outcome measure that incorporates all of the available data. For Aim 1, we will utilize generalized

linear mixed models (GLMM) to model the probability of opioid use across all time points (i.e. Day 7, 15, 30, and 90) as a function of study arm (ACU vs. OPI), time, the arm-by-time interaction, and randomization stratification variables.. For Aim 1 symptom burden, and for the continuous Aim 2 outcome measures, we will use linear mixed models (LMM) to similarly model those continuous endpoints over time. For both the GLMM and LMM analyses, we will use interaction terms between time and study arm to allow us to plot the arm-specific outcome trajectories over time. These statistical procedures (GLMM and LMM) account for within-subject correlations from repeated measurements in the same subjects and allow estimation of between-group differences without necessitating exclusion of participants with missing data.

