**14.3. Missing Data.** We will first explore whether missingness is associated with observed variables (particularly randomization arm and the baseline outcome measures) by comparing patients with complete and incomplete data. Of note, our general longitudinal data analysis approaches described above (GLMM and LMM) validly include patients with incomplete data under the missing at random assumption. However, our exploration of the data may deem the missing at random assumption to be inappropriate, and not all our hypotheses will be tested using these longitudinal modeling approaches. In these cases, we will use well-established methods such as multiple imputation and pattern mixture models to help us deal with these issues. We will perform sensitivity analyses to evaluate the robustness of our main findings by using multiple imputation to impute the missing outcomes (particularly for Day 7 and Day 90) and duplicating the analyses using the multiply imputed data sets.

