#### **14.4 Populations for Analyses**

- Modified Intention-to-Treat Analysis Dataset, Opioid Use: For the Day 7 analysis, this will include all randomized patients who have Day 7 opioid use assessed. For the Day 90 analysis, this will include all randomized patients who have Day 90 opioid use assessed.

- Modified Intention-to-Treat Analysis Dataset, Symptom Burden: This will include all randomized patients who have, at least, a valid baseline MDASI-BMT Total Symptom Severity score.
- Modified Intention-to-Treat Analysis Dataset, Other Continuous Endpoints: For a given continuous endpoint, this will include all randomized patients who have, at least, a valid baseline endpoint measurement.

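### The Hypothesis 2b mixed models have one record per patient, so they are ANCOVAs on observed patients that do not match the stated analysis set and ignore intermediate visits at Day 90

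*Combined protocol and SAP*

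**What the plan says.** - **Section 14.2.3, Hypothesis 2b.** Mean differences with 95% confidence intervals are estimated "using separate linear mixed models for the Day 7 and Day 90 outcomes, controlling for the randomization stratification variables and baseline score (when relevant". The same section calls these covariate-adjusted regressions and quotes 80% power for an unadjusted difference of 0.34 SD at two-sided 0.05.
- **Section 14.2.3, Hypothesis 2a.** The model is a different one: an "LMM containing arm, time (Days 0 and 7), and the arm-by-time interaction as predictors". Baseline is an outcome record here, as it is for Hypothesis 1c in section 14.2.2.
- **Section 14.2.1.** The Aim-specific analyses "focus on single assessment time points, have relatively straightforward interpretations, and will be used to draw our primary conclusions regarding the Aims of this trial". Separately, "for the continuous Aim 2 outcome measures, we will use linear mixed models (LMM) to similarly model those continuous endpoints over time", with arm-by-time terms, mainly to plot trajectories. Mixed models are said to "allow estimation of between-group differences without necessitating exclusion of participants with missing data".
- **Sections 13.2 and 14.4.** A baseline value is enough for inclusion: "For a given continuous endpoint, this will include all randomized patients who have, at least, a valid baseline endpoint measurement".
- **Section 14.3.** It states that "our general longitudinal data analysis approaches described above (GLMM and LMM) validly include patients with incomplete data under the missing at random assumption". It then concedes that "not all our hypotheses will be tested using these longitudinal modeling approaches", and names multiple imputation and pattern mixture models for those cases. Multiple imputation of missing outcomes, chiefly Day 7 and Day 90, is also planned as a sensitivity analysis.

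**The concern.** A mixed model keeps incompletely observed patients because their other outcome records inform the missing one. With Day 7 and Day 90 fitted separately and baseline on the right-hand side, there are no other outcome records. A patient with scores at baseline and Days 7, 15 and 30 but not Day 90 is left out of the Day 90 contrast.

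Two things are at stake. The plan describes the Hypothesis 2b results as resting on every patient with a baseline, and they would not. Also, if patients leave before Day 90 because of how they felt at Day 15 or Day 30, and do so differently by arm, the Day 90 estimates are biased even though the scores that would correct this are collected. The comparator is usual care without sham, so a difference in dropout between arms is plausible.

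**Working it through.** **1. The plan's own figure.** Inputs are 300 randomised 1:1 and 10% attrition, giving 135 per arm (section 14.1, stated for Day 90 opioid use and assumed to apply here), with 80% power and two-sided 0.05. The detectable difference is √(2/n) × (1.960 + 0.842).
- n = 135: 0.1217 × 2.802 = 0.341 SD. Power at 0.34 SD is 79.8%.
- n = 150: 0.1155 × 2.802 = 0.323 SD. Power at 0.34 SD is 83.8%.

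The stated 0.34 SD reproduces with 135 per arm, so the power statement already counts only patients with the outcome observed.

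**2. One record per patient.** With a single outcome per patient, the variance given covariates is σ²(patient) + σ²(residual). Only the sum enters the likelihood. In a simulated data set of 300 patients with 33 outcomes missing, the random-intercept model and ordinary ANCOVA used the same 267 patients and gave the same arm estimate, -0.1648. The log-likelihood was -330.013 however the variance was split. The software warned that the Hessian was not positive definite and reported a standard error of 0.099 against 0.103 from ANCOVA, so the mixed-model standard error is not dependable here.

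**3. Patients in the set but not in the fit.** 300 × 0.10 = 30 at Day 90.

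**4. Which dropout does harm.** Each simulation had 150 per arm, no true effect and 4,000 trials. All correlations and dropout patterns are assumptions.

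*Baseline, Day 7 and Day 90; equal correlation 0.5 or 0.7; about 8 to 11% missing at Day 90.* Bias in SD:
- Dropout on baseline, in opposite directions by arm: baseline-adjusted ANCOVA -0.003 to 0.000. Without baseline adjustment, -0.10 to -0.13.
- Dropout on the Day 7 score in one arm only: ANCOVA -0.019 to -0.026; two-visit model of the Hypothesis 2a form -0.018 to -0.026; model that includes Day 7, about 0.00.

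*All visits; correlation 0.6 between Days 30 and 90, and 0.45 with baseline.* Bias at Day 90 (SD) and two-sided 0.05 rejection:

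| Assumed dropout before Day 90 | One-visit ANCOVA | All-visit model |
|---|---|---|
| Random, 10% | 0.001, 5.2% | 0.001, 5.4% |
| ACU 5% random; OPI 14%, rising with Day 30 score | 0.051, 7.9% | 0.000, 5.0% |
| 8.6% in each arm, opposite directions | 0.044, 7.1% | -0.002, 4.8% |
| Rising with Day 30 score in both arms, 10% v 10% | 0.001, 5.2% | about 0.00 |
| The same, 8% v 12% | 0.014, 4.9% | about 0.00 |
| The same, 5% v 14% | 0.030, 5.8% | about 0.00 |

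Simulation error on a 5% rejection rate is √(0.05 × 0.95 / 4000) = 0.3 percentage points. Raising the Day 30 to Day 90 correlation to 0.7 takes the second row to a bias of about 0.06. Under random dropout the all-visit standard error is about 1% smaller.

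**5. Day 7.** No follow-up visit is scheduled before Day 7, so little information is lost there. No Day 7 bias was simulated.

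**The case against.** The strongest reply is that the plan already deals with this. Section 14.3 ties missing-at-random validity to the general longitudinal models, admits that some hypotheses are tested otherwise, and names multiple imputation or pattern mixture models for those. Section 14.2.1 plans the all-visit model for these outcomes. This stands in part. A reader might infer that section 14.3 promises missing-at-random validity for Hypothesis 2b and is contradicted, or that imputation is only ever a sensitivity analysis. The text supports neither. What remains is that Hypothesis 2b is labelled a mixed model but is not longitudinal, so section 14.3 does not settle which rule governs it. The all-visit model is planned, but the single-visit analyses are the ones that decide.

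A second reply is that the bias needs particular dropout. That is right. With Day 30-driven dropout alike in both arms it vanishes; at 4% v 6%, close to the pilot's 5% attrition, it was 0.008 SD. Even 0.05 SD is small beside 0.34 SD. Hypothesis 2b also has no allocated alpha, so the rejection rates carry limited weight.

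Third, the word separate could mean one model per measure with Days 7 and 90 as joint outcomes. The collapse to ANCOVA would then not apply. Patients with only a baseline would still drop out, and Days 15 and 30 would still go unused. The contrast with Hypotheses 1c and 2a makes the one-record reading the natural one.

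**Conclusion.** The point holds in limited form. On the natural reading, the Hypothesis 2b models are ANCOVAs on patients observed at each visit. They cannot use the baseline-only analysis set of sections 13.2 and 14.4 or deliver the no-exclusion property claimed in section 14.2.1.

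A reader might go further and infer that Hypothesis 2b has no missing-at-random protection. That is not supported: with baseline in the model, the ANCOVA is valid when missingness depends only on arm, baseline and strata. What is lost is validity when Day 90 dropout depends on intermediate scores differently by arm. The resulting bias is about 0.01 to 0.06 SD in the patterns assumed; it is illustrative and not a bound. Leaving baseline out as not relevant would also remove the protection against baseline-dependent dropout.

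Nor is the mixed-model label what separates Hypothesis 2b from Hypothesis 2a: the two-visit Day 90 model there has the same gap. These are secondary outcomes, so the effect on the trial's conclusions is modest. The change is worth making because it is nearly free.

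**What to change.** 1. In section 14.2.3, for each side-effect, PROMIS-29 and PROMS outcome, fit one mixed model with the Day 7, 15, 30 and 90 scores as outcomes, unstructured covariance, arm-by-visit, baseline-by-visit and the stratification factors. Take the Day 7 and Day 90 arm contrasts from it as the Hypothesis 2b estimates. Consider the same for the Day 90 analysis of Hypothesis 2a.
2. Align sections 13.2 and 14.4. Step 1 alone does not do this, because a patient with a baseline and no follow-up still contributes nothing when baseline is a covariate. Either define the set as patients with a baseline and at least one follow-up score, or enter baseline as an outcome record so that baseline-only patients are retained.
3. State in section 14.3 which missing-data rule applies to Hypothesis 2b.

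If the single-visit models are preferred, call them ANCOVAs, always include baseline, define the set as patients observed at that visit, and name the imputation method.

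The cost is wording, slightly more modelling, and a pre-specified fallback covariance structure in case the model does not converge. All four follow-up visits are already scheduled, and no new data are needed.
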